## 17.3 Analysis of participant populations

The participants population whose data will be subjected to the study analysis is dictated by the treatment of intercurrent events. The primary estimand specifies an intention to treat analysis, that is, the outcome data of all recruited and consented participants (no individual participant randomisation) will be included in the main analysis according to their assigned treatment group regardless of their protocol adherence. All clusters will be included in the analysis in the group they were randomised to regardless of their implementation of the intervention. Certain participants may be excluded in sensitivity analyses but no analysis excluding whole clusters is envisaged.

#### 17.4 Primary endpoint analysis

MCS and DRS are co-primary outcomes, that is, the intervention is declared clinically effective only if both primary endpoints are statistically significant. The estimand for both outcomes will be estimated using a linear mixed-effects model with a random intercept for hospital. Restricted maximum likelihood estimation with Kenward-Roger correction will be used. Models will be adjusted for the following individual level baseline covariates (without treatment by covariate interaction) to increase power: age [continuous], surgical procedure [categorical] and Charlson co-morbidity score [ordinal]. MCS will additionally be adjusted for the MCS score at baseline. Missing covariate data will be accounted for using mean imputation [17] for continuous variables and the missing indicator approach [18] for categorical variables. The strategy for accounting for intercurrent events in the analysis models is described in section 6.3 and Appendix 1. If the patient status at 180 days follow-up is 'dead' the outcome values are defined (imputed) as a neutral position on decision regret and a population median for Mental Health Component (DRS=50,

OSIRIS Protocol v2.0 20.11.2023 Page **32** of **46** 

MCS=50). Multiple imputation under missing at random assumption will be used to impute missing outcomes where the participant has not died. Values will be imputed using predictive mean matching with 10 donors and 50 imputations. The complete set of variables included in the imputation model with be specified in the SAP.

The non-inferiority comparison for the MCS will be based on a two-sided 95% confidence interval (equivalent to a one-sided 2.5% alpha level). If the lower bound of the confidence interval is greater than the non-inferiority margin of 3.5, then non-inferiority will be declared. For both co-primary outcomes, we will present a participant-average treatment effect estimate (difference in means between the two treatment groups) along with a confidence interval. The primary outcome Decision regret will be assessed using a superiority test at the conventional 5% alpha level.

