#### 6.1 Primary outcome measure

The co-primary outcome measures are as follows:

OSIRIS Protocol v2.0 20.11.2023 Page **11** of **46** 

• Patients' decision regret at 180 days after the index decision making episode using the Decision Regret Scale (DRS) [12]. The DRS is an easily administered 5-item Likert-type measure written to assess regret or remorse following a medical decision. To help others interpret the score more readily with other scales ranging from 0 to 100, scores are converted to a 0-100 scale by subtracting 1 from each item then multiply by 25. To obtain a final score, the items are summed and averaged. A score of 0 means no regret; a score of 100 means high regret. It has been validated as a useful indicator of health care decision regret at a given point in time [12]. DRS manual:

https://decisionaid.ohri.ca/docs/develop/User\_manuals/UM\_Regret\_Scale.pdf

Patients' mental-health related quality of life at 180 days after the index decision making episode using the Mental Component Summary (MCS) score of the Short Form-12 (SF-12) Health Survey with UK derived weightings [13, 14]. The SF-12 Health Survey is a generic health-related quality-of-life instrument. It was originally developed in 1994 as a shorter alternative (12 items) to the widely used Short-Form 36 Health Survey, for studies in which a 36-item form was too long. The items of the SF-12 were selected to reproduce the two summary measures, Physical Component Summary (PCS) and Mental Component Summary (MCS), of the SF-36. The SF-12 mental component summary (MCS-12) scoring method proposed by Ware et al will be used, [15] this assumes that each item contributes to both physical component summary and that these two measures are uncorrelated. Validation studies have shown the SF-12 yielded acceptable results for detecting both active and recent depressive disorders in general population samples. MCS-12 use norm-based scoring, where the mental summary measures have a mean of 50 and an SD of 10 in the general population and scores greater than 50 reflect better mental health status than the general population and scores lower than 50 worse mental health.

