#### Baseline data

BMI category

- Laboratory data (preoperative haemoglobin, estimated glomerular filtration rate)
- Co-morbid disease including mental illness
- Quality of life according to EQ-5D-5L
- 12-Item Short Form Survey

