## 17. Statistical and data analysis considerations

## 17.1 Sample size calculation

The sample size calculation is considering both primary endpoints individually. The unit of randomisation is hospitals and an intra-cluster correlation of 0.01 within hospitals is assumed for each outcome. Furthermore 20% loss to follow-up at the individual participant level is assumed at the primary outcome time point of 180 days. No clusters are anticipated to drop out. For the non-inferiority comparison of the MCS a noninferiority margin of 3.5 points is chosen. A standard deviation (sd) of 11 is assumed for MCS [75] which means that the margin corresponds to approximately 30% of the sd. Accounting for clustering, 460 participants would be needed to demonstrate noninferiority with 90% power and a one-sided 2.5% significance level if there truly is no difference in MCS between groups. This equates to a recruitment target of 40 hospitals recruiting 15 participants each after accounting for loss to follow-up, i.e. 600 in total. The minimum clinically relevant difference on the DRS is a 7.5 point between-group difference in mean scores. The literature suggests a standard deviation of 16 for DRS [67] which means that the 7.5 point difference corresponds to a small to medium effect size. With the sample size required for the non-inferiority comparison and again accounting for clustering this difference can be detected with 99.8% power at the 5% significance level for a two-sided superiority test. The overall power to reject the null hypotheses for both primary outcomes is at least 89.8%.

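### Baseline MCS is collected and already used for the MCS model, and adding it to the DRS model in Protocol 17.4 would be a nearly free gain in precision

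*Protocol*

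**What the plan says.** Section 17.4 of the protocol fits a linear mixed model with a random hospital intercept to each co-primary outcome. Both models carry age, surgical procedure and Charlson score, described as "individual level baseline covariates (without treatment by covariate interaction) to increase power". Then: "MCS will additionally be adjusted for the MCS score at baseline". Nothing is added for DRS. Missing continuous covariates are mean-imputed.

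The baseline data list in section 12.4 includes the "12-Item Short Form Survey" and "Quality of life according to EQ-5D-5L". The schedule in 12.1 places the baseline SF-12 at the pre-surgical/surgical clinic, the column before the index decision episode at which the aid is used. DRS appears in that schedule only at 180 days.

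Section 17.6 lists two sensitivity analyses for the primary estimands: one without participant covariates, and one with clustering by doctor within hospital. The four further analyses there change the handling of missing data, surgery status, adherence or deaths. None adds baseline MCS to the DRS model.

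On size, section 17.1 says: "The minimum clinically relevant difference on the DRS is a 7.5 point between-group difference in mean scores". It also says: "The literature suggests a standard deviation of 16 for DRS".

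**The concern.** DRS cannot have a baseline of its own, because there is no decision to regret before the decision is made. Its model therefore contains no patient-reported baseline measure. Baseline mental health is a plausible predictor of later regret, although the protocol gives no evidence on this. Age, procedure and Charlson score do not measure it.

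DRS carries the superiority claim, and the intervention is declared effective only if both co-primaries succeed. Forty hospitals are randomised without stratification (12.2), so the arms may differ somewhat in baseline mental health by chance. The MCS comparison would be corrected for such a difference, but the DRS comparison in the same patients would not. What is at stake is the width of the DRS confidence interval and how easily the DRS result can be read if a baseline MCS difference is seen.

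**Working it through.** **Inputs from the protocol (12.2, 17.1).** MCS margin 3.5, SD 11, 90% power, one-sided 2.5%. DRS difference 7.5, SD 16, two-sided 5%. ICC 0.01 for each outcome. 40 hospitals of 15, allocated 1:1. 20% loss, so 600 × 0.8 = 480 analysed, or 12 per hospital.

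**Assumed, not in the protocol.** The correlation r between baseline MCS and 180-day DRS given the other covariates (0.1 to 0.4), and an ICC of 0.01 for baseline MCS. Normal approximations are used throughout.

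**Step 1: reproduce the plan's figures.**
- Per arm without clustering: 2 × [11 × (1.960 + 1.282)/3.5]² ≈ 207.6, rounded up to 208.
- Design effect: 1 + (12 − 1) × 0.01 = 1.11. Total analysed: 461 to 462, against the stated 460.
- With 20% loss: 461/0.8, rounded up to 577, which 600 covers.
- DRS standard error at 480: effective n per arm 240/1.11 = 216.2, so 16 × √(2/216.2) = 1.54.
- DRS power: Φ(7.5/1.54 − 1.96) = 99.8%, as stated.
- Joint power, lower bound: 0.90 + 0.998 − 1 = 0.898, as stated.

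**Step 2: add baseline MCS to the DRS model.** The residual SD becomes 16 × √(1 − r²).

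| r | SE | SE reduction | 95% CI half-width | Power at 7.5 | Power at 5 (illustrative) |
|---|---|---|---|---|---|
| none | 1.54 | – | 3.02 | 99.8% | 90.1% |
| 0.1 | 1.53 | 0.5% | 3.00 | 99.8% | 90.4% |
| 0.2 | 1.51 | 2.0% | 2.96 | 99.9% | 91.2% |
| 0.3 | 1.47 | 4.6% | 2.88 | 99.9% | 92.6% |
| 0.4 | 1.41 | 8.3% | 2.76 | 99.96% | 94.4% |

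**Step 3: shift given a chance imbalance.**
- SD of the between-arm difference in baseline MCS: 11 × √(4 × 1.11/480) = 1.06 points. A 1.96-SD imbalance is 2.1 points.
- Slope of DRS on MCS: r × 16/11, or 0.145 at r = 0.1 and 0.58 at r = 0.4.
- Shift in the DRS difference: 0.145 × 2.07 = 0.3 points, and 0.58 × 2.07 = 1.2 points.
- With a baseline ICC of 0.05, the 1.96-SD imbalance is 2.45 points. The shift at r = 0.4 is then 1.4 points.

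**Step 4: steps 2 and 3 describe one quantity.** At r = 0.4 the shift for a 1-SD imbalance is 0.62, and 0.62² ≈ 0.38. The adjusted variance is 1.41² ≈ 1.99. Their sum, 2.37, is the unadjusted variance 1.54². So the unadjusted standard error already contains the chance-imbalance shift. Adjustment removes that component; it does not correct an additional error.

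**The case against.** The strongest reply is that nothing here is wrong. Section 17.4 uses one common covariate set and adds an outcome's own baseline where one exists. DRS has none, and different covariates for different outcomes are ordinary practice. In a linear model without treatment-by-covariate interaction, adding a covariate does not change the target difference in means. The stated aim of adjustment is power, and DRS already has 99.8% without covariates. Joint power is limited by MCS, whose model already includes its baseline. All of this stands.

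A reader might infer more in three ways, and the protocol does not support any of them.
- *That the DRS estimate is biased or unprotected.* Under randomisation, omitting a prognostic covariate leaves the estimate unbiased, and chance imbalance is already inside the standard error (step 4). Three patient-level covariates are also in the model. For the same reason, the 0.3 to 1.2 point shift should not be set against the roughly 3-point significance threshold as if it were extra error.
- *That the DRS test is underpowered.* At 7.5 points the covariate adds less than 0.3 percentage points of power.
- *That open recruitment makes the arms differ systematically in mental health.* Patients are recruited within hospitals in an open trial, so this is possible. The protocol gives nothing from which to size it, and the point does not rest on it.

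It is also fair to say that the gain depends on an unknown r. At r = 0.1 to 0.2 the standard error falls by 2% or less. A further sensitivity model could sit in the SAP, which is not at hand, so its absence there cannot be counted. The covariate list itself, however, is fixed in 17.4.

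**Conclusion.** The point holds as a low-severity improvement. The protocol leaves out of the DRS model a baseline measure that it collects before the intervention, uses in the other co-primary model, and already has a missing-data rule for. Using it serves the protocol's own reason for adjusting. The benefit is modest: a confidence-interval half-width of 3.00 to 2.76 instead of 3.02, and 90.4% to 94.4% power instead of 90.1% if the true effect were 5 points. A DRS result read alongside an observed baseline MCS difference would also need no caveat about that difference. These figures rest on the assumed r of 0.1 to 0.4 and, for the imbalance, on a baseline ICC of 0.01. If r is near zero, almost nothing is gained or lost.

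**What to change.** In section 17.4, before unblinding, add baseline MCS (from the SF-12 completed before the aid is used) as a continuous covariate in the DRS model, with the mean imputation already specified for missing continuous covariates. Carry the same wording into the SAP. If the sponsor prefers to keep the primary DRS model as it stands, pre-specify the adjusted model as a sensitivity analysis in 17.6. Either must be fixed before allocation is known to the analyst, since a later addition would look data-driven. The cost is one phrase and one patient-level degree of freedom. No new data are needed, and neither the sample size nor the estimand changes.

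### Section 17.4 states the MCS non-inferiority bound as +3.5 instead of -3.5 and does not fix the order of subtraction, contradicting sections 6.3.2 and 17.1

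*Protocol*

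**What the plan says.** Section 17.4 of the protocol bases the MCS comparison on a two-sided 95% confidence interval, treated as a one-sided 2.5% test, and then states: "If the lower bound of the confidence interval is greater than the non-inferiority margin of 3.5, then non-inferiority will be declared". The same section describes the treatment effect only as a difference between the two group means, without saying which group is subtracted from which. It also requires both co-primary outcomes to succeed before the intervention is called clinically effective.

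Three other places bear on how the rule should read:

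- Section 6.1 sets the direction of the scale: "scores greater than 50 reflect better mental health status than the general population". Higher is better.
- Section 6.3.2 gives the MCS objective as non-inferiority of the decision support intervention to best standard care.
- Section 17.1 says "a noninferiority margin of 3.5 points is chosen" and sizes the trial "to demonstrate noninferiority with 90% power and a one-sided 2.5% significance level if there truly is no difference in MCS between groups".

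**The concern.** On a scale where higher is better, non-inferiority means ruling out a deficit larger than the margin. For intervention minus control, the confidence interval must lie wholly above -3.5. The sentence in section 17.4 instead requires it to lie wholly above +3.5, which is a demonstration that the intervention improves MCS by more than 3.5 points. That is a different and much harder hypothesis than the one in section 6.3.2.

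This sentence is the only explicit pass/fail rule for MCS in the protocol, and MCS is one of two outcomes that must both succeed. Applied literally, an intervention that reduced decision regret and left mental health unchanged, which is the scenario the trial was sized for, would almost certainly be reported as not having met its MCS criterion. MCS is also the outcome that guards against the distress acknowledged in section 7.3, so its rule should be beyond doubt. Several sensitivity analyses in section 17.6 are defined by reference to section 17.4 and point back to the same text.

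**Working it through.** **Inputs**

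- From section 17.1: margin 3.5 points, SD 11, intra-cluster correlation 0.01, 20% loss to follow-up, no loss of clusters, 40 hospitals recruiting 15 each, 90% power, one-sided 2.5%, true difference zero.
- From section 12.2: 1:1 allocation of hospitals.
- Derived: 15 × 0.8 = 12 analysed per hospital, so 40 × 12 = 480 in total.

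**Step 1: reproduce the plan's own figure.** Without clustering, and with the null hypothesis at -3.5:

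- n per arm = 2 × [11 × (1.960 + 1.282) / 3.5]² = 207.6, or 415.15 in total before rounding.
- Design effect = 1 + (12 - 1) × 0.01 = 1.11.
- Total = 415.15 × 1.11 = 460.8.

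The protocol states: "Accounting for clustering, 460 participants would be needed". The figures agree. Allowing for loss gives 460.8 / 0.8 = 576, which 40 hospitals of 15 (600) covers. The distance from the assumed truth (zero) to the null value in this formula is 3.5, and the favourable side is upward, so the test that was sized has its bound at -3.5.

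**Step 2: standard error.** SE = 11 × √(4 × 1.11 / 480) = 1.058.

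**Step 3: chance of meeting each rule when the true difference is zero** (normal approximation, intervention minus control)

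- Bound at -3.5: Φ(3.5 / 1.058 - 1.96) = Φ(1.35) = 0.911.
- Bound at +3.5, as written: 1 - Φ(3.5 / 1.058 + 1.96) = 1 - Φ(5.27) = 6.9 × 10⁻⁸.

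With 460 analysed instead of 480, the two figures are 0.899 and 1.0 × 10⁻⁷.

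**Step 4: what the written rule would require**

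- Smallest passing observed difference: 3.5 + 1.96 × 1.058 = 5.6 points, about half an SD. With the bound at -3.5 it is -3.5 + 1.96 × 1.058 = -1.4 points.
- True difference for 90% power: 3.5 + (1.96 + 1.282) × 1.058 = 6.9 points.

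| True MCS difference | P(lower bound > +3.5) | P(lower bound > -3.5) |
|---|---|---|
| 0 | 7 × 10⁻⁸ | 0.911 |
| +1 | 8 × 10⁻⁶ | 0.989 |
| +2 | 0.0004 | 0.999 |
| +3.5 | 0.025 | above 0.999 |
| +5 | 0.29 | above 0.999 |
| +7 | 0.91 | above 0.999 |

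**Step 5: does reversing the subtraction rescue the sentence?** No. For control minus intervention, a positive value is a deficit on the intervention, and the correct rule would be an upper bound below +3.5. The written rule uses the lower bound and asks for it to be above 3.5, so it is not a non-inferiority test in either order.

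**The case against.** The strongest reply is that this is a margin quoted as an absolute value and nobody would apply it literally. Section 17.1 gives 3.5 as a magnitude, about 30% of the SD, and its sample size reproduces with the bound at -3.5. Section 6 speaks of not harming mental health-related quality of life, and section 17.4 itself calls the comparison non-inferiority. That stands as evidence of intent. It does not make the stated rule correct, and the sign of a primary test should not be left to inference.

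A second reply is that section 17.2 makes the SAP the principal analysis document. The SAP is not available here, so whether it has the right sign cannot be checked. This is not a detail deferred to the SAP, though: the protocol states the rule and states it wrongly. If the SAP is right, the two documents disagree on a success criterion. If it copied section 17.4, it carries the error.

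A third is that the machine-readable text drops some line-end hyphens (non-inferiority loses its hyphen in section 17.1), so a minus sign could have been lost the same way. That is possible but unproven, and the typeset page would settle it. The order of subtraction would still need stating.

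Two stronger readings are tempting and should be resisted:

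- A reader might infer that the MCS criterion can never be met and the trial cannot succeed. The very small probability holds at a true difference of zero. The written rule would pass about nine times in ten if the true benefit were near 7 points, although nothing in the protocol assumes such a benefit.
- A reader might infer that the rule could declare non-inferiority when the intervention is proven worse, by taking control minus intervention. Section 6.3.2 compares the intervention with standard care, and section 17.4 uses the lower bound on a higher-is-better scale. Both point to intervention minus control, so that reading has little support.

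**Conclusion.** The success criterion for MCS in section 17.4 is wrong as written. It has the wrong sign, leaves the order of subtraction unstated, and contradicts sections 6.3.2 and 17.1. Under the planning assumption of no true difference, applying it literally would turn a success probability of about 91% into one of about 7 × 10⁻⁸. Because both co-primary outcomes are required, that would also settle the overall conclusion.

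These figures rest on the protocol's SD and intra-cluster correlation, 480 analysed, and a normal approximation without covariate adjustment. A t reference with 38 degrees of freedom gives 89.7% at -3.5, and the smallest passing difference under the written rule stays at 5.6 points. Any precision gained from adjusting for baseline MCS would make the written rule even less likely to be met at zero difference.

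This is an error in the stated rule and not in the design. The intended bound can be recovered from section 17.1, and the sample size and planned power are unaffected. It still has to be corrected, because it is the stated criterion for a co-primary outcome.

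**What to change.** Replace the sentence in section 17.4 with:

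> The difference is intervention minus control. Non-inferiority is declared if the lower limit of the two-sided 95% confidence interval is greater than -3.5.

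Check that the SAP carries the same rule, with the same sign and order of subtraction. Make the change before the allocation code is released to the trial statistician, so that it cannot be seen as a response to the results.

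The cost is a one-sentence protocol amendment under section 21.3, and a matching line in the SAP if it is not already there. The sample size, analysis model, estimand and data collection do not change.

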## 17.5 Subgroup analysis

Subgroup analyses will be conducted by fitting an interaction term between the study group indicator variable and the variable defining the subgroup in the primary outcome analysis model. The following subgroup analyses are currently planned:

- Surgical procedure (colorectal bowel resection for cancer, hip-replacement, abdominal aortic aneurysm surgery)
- Patient gender
- Ethnicity

Other subgroup analyses may be added in the future and be pre-specified in the SAP prior to the final statistical analysis commencing.

#### 17.6 Planned sensitivity analysis

There are two planned sensitivity analyses that target the primary estimands.

- 1. Unadjusted analysis accounting for clustering by hospital but no individual participant characteristics including planned surgery
- Model assuming clustering by doctor involved in index decision making episode within hospital

Four sensitivity (secondary) analyses which target different estimands involving the primary outcomes are planned. The estimands for these analyses will be fully specified in the SAP

 An analysis as described in 17.4 using all available data without imputation of outcomes (imputation of co-variates only)

OSIRIS Protocol v2.0 20.11.2023 Page **33** of **46** 

- 2. An analysis as described in 17.4 but excluding all participants whose surgery has been cancelled or delayed by more than 180 days. A principle stratum approach is used for these intercurrent events in which the treatment effect is estimated in the subpopulation of patients in which the event didn't occur. This estimate is unbiased under plausible assumptions [19].
- An analysis as described in 2 but additionally excluding participants who did not initiate their assigned intervention as planned. This is akin to a per-protocol analysis.
- 4. An analysis as described in 17.4 assuming a range of more negative values of DRS and MCS for participants who died within the 180 days follow-up.

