#### 12.7 Control

In control group hospitals, shared decision making for high-risk patients will follow current local practices. There will be no additional training or changes to care processes for these sites.

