#### 14.5 Assessment of compliance

The device will be used only by trained investigators during the clinical study, Use of the device will be recorded within the study documentation, non-use of the device for consented patients in intervention sites will be recorded as a protocol deviation.

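### Secondary analysis 2 rests its unbiasedness on an unnamed and doubtful assumption about who is cancelled or delayed, and analysis 3 adds an exclusion that in practice only intervention patients can meet

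*Protocol*

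**What the plan says.** Section 17.6 separates two sensitivity analyses that target the primary estimands from a second list, introduced thus: "Four sensitivity (secondary) analyses which target different estimands involving the primary outcomes are planned". This point concerns items 2 and 3 of that second list.

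- **Analysis 2** repeats the primary model "excluding all participants whose surgery has been cancelled or delayed by more than 180 days". It is described as a principal stratum approach in which "the treatment effect is estimated in the subpopulation of patients in which the event didn't occur". The section then adds: "This estimate is unbiased under plausible assumptions [19", citing reference 19. The assumptions are not listed. By its title, that reference concerns failure to initiate treatment.
- **Analysis 3** starts from analysis 2, "additionally excluding participants who did not initiate their assigned intervention as planned. This is akin to a per-protocol analysis". No claim of unbiasedness is attached to it.

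Other sections bear on who can be excluded:

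- Section 5 presents the aid as informing decisions about surgery, and Section 6 places the choice to proceed or not at the index episode.
- Section 12.10 states that patients and the staff delivering the intervention are unblinded.
- Section 8.2 allows patients to be found from operating theatre lists as well as clinic lists.
- Section 14.5 says "non-use of the device for consented patients in intervention sites will be recorded as a protocol deviation". In control hospitals, under Section 12.7, "shared decision making for high-risk patients will follow current local practices".

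The primary estimands (Sections 6.3.1 and 6.3.2) count patients whether or not surgery was delayed or took place. Section 17.3 analyses all consented participants by assigned group.

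**The concern.** Both exclusions act on events that happen after randomisation. Dropping patients with the event from each arm compares like with like only if the same patients would have had it under either allocation.

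For analysis 2 that is hard to take for granted. If declining surgery counts as a cancellation, which is possible for a patient already on a theatre list, the aid acts on the event directly. If declining does not count, the aid can still change who chooses surgery, and only those who choose it can later be cancelled or delayed. On either reading, an aid that changes decisions can change who is excluded.

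For analysis 3 the added exclusion is in effect one-sided. Control patients receive local practice and have nothing new to initiate, so intervention patients are filtered and controls are not. If the aid is withheld more often from patients who seem distressed (my inference; Section 14.11 has the clinician elicit worries first and watch for distress), the filter is related to MCS.

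At stake is how two secondary results are interpreted. A per-protocol result beside a non-inferiority comparison is easily taken as support, and this one could look favourable or unfavourable with no true effect.

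**Working it through.** **The plan's figures.** Section 17.6 gives no number. The yardsticks come from Section 17.1: DRS difference 7.5 with SD 16, MCS margin 3.5 with SD 11, ICC 0.01, 40 hospitals of 15 with 20% loss (12 analysed per hospital, 480 in all). That section's own figures reproduce. The MCS comparison needs 2 × (11 × (1.960 + 1.282)/3.5)² ≈ 207.6 per arm. Doubling and multiplying by the design effect 1 + 11 × 0.01 = 1.11 gives 460.8, against 460 stated. Then 460.8/0.8 = 576, or 14.4 per hospital, rounded up to 15.

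**Assumed inputs.** The protocol gives no cancellation, delay or non-initiation rates, and no outcome differences for those patients. All such inputs below are assumptions. The true effect is set to zero throughout, and d is the mean outcome difference left after covariate adjustment.

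**Analysis 2, extra events under the intervention.** Let p0 be the control event rate, e the share with the event only under the intervention, and d the amount by which that group's DRS exceeds that of patients with no event in either arm. The control arm keeps the group and the intervention arm loses it, so

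bias = −[e/(1 − p0)] × d.

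With d of 8 to 16 points (half to one SD) and p0 of 10% to 20%:

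| e | Bias, DRS points | Largest, as share of 7.5 |
|---|---|---|
| 0% | 0 | 0% |
| 5% | −0.4 to −1.0 | 13% |
| 10% | −0.9 to −2.0 | 27% |
| 15% | −1.3 to −3.0 | 40% |

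For example, 0.15/0.80 × 16 = 3.0. With e = 10%, a two-sided 5% test would reject about 8% to 21% of the time.

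**Analysis 2, extra events under control.** Suppose 10% of patients are reluctant, with DRS 20 points above the rest. All of them cancel under control. With the aid, 4% of patients cancel, while 6% decline at the index episode and are kept. The intervention arm then shows an excess of 20 × 0.06/0.96 = +1.25 points, 17% of 7.5. With 15% reluctant and 5% cancelling, 20 × 0.10/0.95 = +2.1 points, 28%. The sign is now against the aid.

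**Simulation check** (40 hospitals of 12):

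- No effect of allocation on the event: bias 0.06, rejection 4.7%.
- e = 10%, p0 = 10%, d = 16: bias −1.75 (formula −1.78), rejection 17%.
- Equal event rates but different patients: 10% have the event only under the intervention (DRS 16 above the rest), 10% only under control (16 below) and 5% under both. Bias is −3.7; by formula, −2 × 16 × 0.10/0.85 = −3.76.

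The last case is extreme, but it shows that balanced exclusion counts would not establish the assumption.

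**Analysis 3, added exclusion alone.** With a share q not initiating in the intervention arm and none in control, bias = −q × d, where d is the non-initiators' mean minus the initiators'. For MCS, with q from 5% to 30% and d of 5.5 to 11 points in size (half to one SD), the bias is 0.05 × 5.5 = 0.28 to 0.30 × 11 = 3.3 points, or 8% to 94% of the 3.5 margin. It favours non-inferiority if non-initiators have worse MCS, and counts against it if they have better. The upper end is harsh, because the MCS model adjusts for baseline MCS (Section 17.4).

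**The case against.** The strongest reply is that the protocol's claim is conditional. It says unbiased under assumptions, and where allocation leaves the event alone the exclusion does work, as the first simulation shows. A reader might infer from this point that the protocol asserts something shown to be false. The documents do not support that: the defect is that the assumption is not named and is doubtful in this design. Nor does the unbiasedness sentence extend to analysis 3, which is only likened to a per-protocol analysis.

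A reader might also infer that the trial's conclusion is at risk. It is not. Effectiveness is declared on the Section 17.4 analysis of all consented participants, and Section 17.6 labels these analyses secondary with different estimands.

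Two further objections stand in part. First, the aid is meant to inform the decision to proceed; nothing says it is meant to alter later cancellation or delay, which may be administrative. Device non-use may likewise follow network failure (Section 14.9) and be unrelated to outcome. Such events add little bias, which is a reason to record causes. Second, the estimands are left to the SAP, and intercurrent-event handling is referred to an Appendix 1 that is not in the text available. That may supply definitions, but the protocol already fixes the estimator as exclusion and calls its assumptions plausible.

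The sizes are illustrations, and the two analysis 2 scenarios point in opposite directions.

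**Conclusion.** The point holds for the two secondary analyses only. Analysis 2 needs allocation not to affect which patients are cancelled or delayed. The protocol does not say so, and an open trial of an aid to the surgery decision gives reason to doubt it. Analysis 3 compares selected intervention patients with controls not selected in the same way.

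The direction of bias is not established. For analysis 2 it is zero if the assumption holds, and illustratively about 1 to 3 DRS points if some 6% to 15% of patients have the event under one allocation only. That rests on assumed gaps of 8 to 20 points between those patients and the rest. For analysis 3 the MCS illustration spans a small to a near-complete share of the margin, driven by the assumed non-initiation rate. The treatment-policy primary analyses, the co-primary decision and the sample size are unaffected. It should be corrected before the analyses are run.

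**What to change.** 1. Delete the unbiasedness sentence, or replace it with the explicit assumption that allocation does not affect who has the excluding event, and say that it may fail here.
2. Define cancelled as distinct from declined at the index episode. Record the reason for cancellation or delay: Section 12.4 lists no such item and codes patients without surgery as not applicable. Tabulate exclusions by arm and reason.
3. In analysis 2, keep cancellations decided by patient or clinician and exclude only hospital-initiated ones. State that this reduces the dependence on who chose surgery but does not remove it.
4. Label analysis 3 as subject to one-sided selection and not as support for MCS non-inferiority.
5. Optionally add a complier-average estimate that retains all participants, using hospital allocation as the instrument and recorded device use as the exposure. State that its assumption of no effect of training alone is strong, since Section 12.6 makes training part of the intervention. It will also be less precise than simple exclusion.

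The cost is one extra CRF item, some protocol and SAP wording, and a less favourable description of two secondary analyses.
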